Screening for eligibility and consenting will take place once the patient has been accepted for kidney transplantation at the University of Colorado Hospital by the Transplant Surgery team. Randomization will occur after patients consent for the study. Only the PI will remain unblinded to the group allocation (see below).

Preoperative data will be collected by the blinded investigator (study coordinator), including baseline vital signs (including room air SpO₂), comorbidities, medications, and kidney graft relevant factors. The baseline dyspnea scores will be assessed by asking patients to complete the PROMIS® v1.0 Dyspnea Functional Limitations Short Form 10a_9-2-2016 questionnaire (available at http://www.healthmeasures.net/administrator/components/com_instruments/uploads/PROMIS%20SF%20v1.0-Dyspnea%20Functional%20Limitations%2010a_9-2-2016.pdf). This is a validated and standardized short questionnaire to quantitate if sugammadex used for NMBR reduces the subjective dyspnea scores relative to baseline.

Intraoperative phase

We will perform a prospective parallel randomized study of rocuronium/sugammadex (intervention) vs. rocuronium/neostigmine (control) for NMB and NMBR at the end of kidney transplantation surgery. This will be performed by the unblinded investigator, following the following protocol(s):

- A quantitative TOF (qTOF) monitor (the Stimpod NMS450®, Xavant Technology Ltd., South Africa, the acceleromyography-based monitor available at UCH, and/or the TwitchView™, Blink Device Company, Seattle, WA, an electromyography-based monitor) will guide the NMB and NMBR management in all study patients. Quantitative NMB monitoring are considered superior to the more routinely-used but subjective qualitative TOF monitors[34, 35]. The qTOF monitor will be placed in the ulnar nerve territory to stimulate the adductor pollicis muscle[36] immediately after loss of consciousness during induction of anesthesia. The exact location of monitoring will be marked and used for qTOF measurements in the postoperative period.
- NMB brief protocol: Rocuronium will be the NMB agent used in both groups as guided by the qTOF and following standard dosing protocols in order to achieve adequate NMB to allow the intubation and surgical procedure (routinely T4/T1 < T3 until closure of surgical incision). Rocuronium dosing: 0.6-1.2 mg/kg for intubation, 0.08-0.2 mg/kg bolus for maintenance with recovery of second twitch (T2) in qTOF.

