Incidence of residual or recurrent NMB in the postoperative floor. This will be calculated as described before (T4/T1 <0.9 , considered severe if T4/T1 <0.4), as an average of 3 repetitions obtained on two occasions separated by ≥ 6 h daily on postoperative days 1-3 or until the end of monitoring criteria have been met.

Morphine equivalents will be calculated from individual opioid doses administered to each patient following standard conversion formulas[21, 40]. This morphine equivalent dose will be calculated for the PACU period and daily for 3 first postoperative days or until the end of monitoring criteria have been met, and used as covariate in the logistic regression analysis.

Time from NMBR administration to quantitative TOF T4/T1 >0.9 (minutes, one decimal). The quantitative TOF will be repeated at 80 mA every 30 seconds from the moment the NMBR medication (sugammadex or neostigmine) has been completely administered intravenously.

Time from NMBR administration to extubation (minutes, once decimal).

Time of total operating room time (minutes), counting from in-room time stamp to out-of-room time stamp.

The PROMIS® v1.0 Dyspnea Functional Limitations Short Form 10a_9-2-2016 questionnaire is a validated and standardized short questionnaire to quantitate if sugammadex used for NMBR reduces the subjective dyspnea scores relative to baseline. It will be completed by the patient in the preoperative phase and during the postoperative follow up. It is available at http://www.healthmeasures.net/administrator/components/com_instruments/uploads/PROMIS%20SF%20v1.0-Dyspnea%20Functional%20Limitations%2010a_9-2-2016.pdf.

Postoperative Pulmonary Complications (PPCs) following previous definitions[13, 41, 42], including:

Respiratory Failure, defined as[41]: "When postoperative $\text{PaO}_2 < 60\text{mmHg}$ on room air, a ratio of PaO_2 to inspired oxygen fraction < 300 or arterial oxyhemoglobin saturation measured with pulse oximetry (SpO_2) $< 90\%$ and requiring oxygen therapy".

Unplanned intubation with postoperative mechanical ventilation (POMV), defined as placement of a breathing tube that was not intended or planned, excluding instances of intubation during an unplanned return to the operating room. Also excluded those patients that were transferred intubated and ventilated to the intensive care unit (ICU) from the operating room.

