Kidney graft outcomes, including postoperative ClCr, daily urine output, need for dialysis postoperatively, diagnosis of delayed graft function, kidney graft rejection. Postoperative hemodialysis is not usually planned and typically reserved for patients with immediate donor graft failure who exhibit signs of congestive heart failure within the first week after transplantation. The need of rescue hemodialysis within the first week after kidney transplantation is an accepted and simple definition of delayed kidney graft function[46].

Hospital resources utilization: hospital floor length of stay (LOS) (days, rounded to half a day), ICU admission and LOS, estimated cost based on average daily cost at a postoperative UCH floor or ICU and/or based on reported estimated costs per PPC[47, 48]

Hypersensitivity adverse events: hypersensitivity signs and symptoms, including but not limited to rash, bronchospasm or anaphylaxis, will be obtained for up to 3 postoperative days directly from the patient and the patient's providers. Their relationship to sugammadex will be assessed by the patient's physicians and the study safety officer. Their confirmatory testing and management will be performed strictly at the discretion of the patient's physicians.

Statistical Methods

The primary hypothesis is that the frequency of patients with one or more episodes of hypoventilation events in PACU (% of patients) is lower in the sugammadex group compared to neostigmine (controls). This will be analyzed by logistic regression which includes as covariates group allocation, total morphine equivalents, and TOF T4/T1 response, and other observed significant and clinically relevant differences between the groups. The odds ratio for the group covariate will be the primary outcome of interest, with the other covariates included in the model to adjust for potential confounders related to hypoventilation.

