The secondary analysis comparing delayed efficacy of sugammadex to neostigmine in reducing the incidence of hypoventilation during the first 3 postoperative days will assume the same model and covariates as the primary hypothesis. To compare the incidence of PPCs a logistic regression model will be used with the binary outcome of any PPC and will include covariates for group and total morphine equivalents. Hospital length of stay and costs will be compared between groups using a linear regression model including covariates for group, total morphine equivalents, presence of respiratory comorbidities and other clinical differences that may influence the outcome. Continuous outcomes may be transformed if they violate the normality assumption (e.g., a log-transformation).

Multiplicity

Given only one primary outcome and hypothesis, there is a not a concern for multiplicity. Secondary analyses are considered exploratory in this protocol.

Power/Sample Size:

Based upon a sample size of 40 patients per group, this study has 90% power to detect a 50% difference in hypoventilation incidence in the PACU (from 76% as reported in previous studies[21] to 38%, alpha 0.05), assuming a potential dropout of up to 6 patients per group. The 50% reduction is considered clinically relevant for a decrease in the frequency of hypoventilation, a precursor of more clinically significant complications such as hypoxemia, reintubation or pneumonia. Quantifying the contribution of hypoventilation into more severe complications is challenging, and details of duration and severity of hypoventilation are not well known. Thus, only a significant reduction in hypoventilation incidence (i.e. 50%) may be accepted as relevant. This trial will provide additional detailed information that may provide more insight on the clinical consequences of hypoventilation (e.g. potential association between accumulated minutes of MV <40% expMV and decrease in SpO₂/FiO₂ over the following 30 min).

A sample size of 40 patients per group would also have approximately 80% power (78%) to detect a difference in case the incidence of any hypoventilation events is 60%, instead of the literature-based 76%. The table below provides the sample size per group to achieve a variety of assumptions for the primary outcome, alpha, and power:

Incidence Group 1	Incidence Group 2	Alpha	Power	Sample Size per Group
1. 0.76	2. 0.38	3. 0.01	4. 0.8	5. 39
6. 0.76	7. 0.38	8. 0.05	9. 0.8	10. 26

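### The model for any postoperative pulmonary complication (PPC) adjusts only for postoperative opioid dose; one pre-specified baseline covariate in its place would be a small, free improvement

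*Combined protocol and SAP*

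**What the plan says.** The Statistical Methods part of section III.F gives any PPC a "logistic regression model will be used with the binary outcome of any PPC and will include covariates for group and total morphine equivalents". Length of stay and cost, in the next sentence, get a "linear regression model including covariates for group, total morphine equivalents, presence of respiratory comorbidities and other clinical differences that may influence the outcome". The primary model, in the paragraph before, adds to its named covariates "and other observed significant and clinically relevant differences between the groups". The PPC model has no such clause and no comorbidity term.

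Under Variables/Time Points of Interest, the opioid covariate is defined as follows: "This morphine equivalent dose will be calculated for the PACU period and daily for 3 first postoperative days". The Preoperative phase of section III.C lists as collected before surgery "baseline vital signs (including room air SpO₂), comorbidities, medications, and kidney graft relevant factors". On allocation, the same section says "Randomization will occur after patients consent for the study"; it names no stratification factor.

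The Multiplicity paragraph labels secondary analyses exploratory. Section III.E concedes that the sample may be too small for clinical complications.

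**The concern.** Two things stand out when the covariate lists are read together. The only adjuster in the PPC model is measured after randomisation and after the reversal drug has been given, so treatment may influence it and it cannot correct a baseline difference. And a baseline variable with an obvious link to pulmonary complications is used for length of stay and cost but left out of the pulmonary outcome, without a stated reason.

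The stake is the reading of one secondary result. If one arm happens to hold more patients with respiratory disease, the PPC odds ratio will carry part of that difference, and the pre-specified model cannot remove it. A covariate added after the imbalance has been seen would be open to the charge of selection. Some power is also forgone.

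**Working it through.** **Inputs.** From the documents: 40 patients per group (Power/Sample Size), the covariate lists, and the timing of each variable. The documents give no PPC rate, no comorbidity prevalence and no strength of any predictor. All of these are assumptions below, shown as ranges.

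**The plan's own figure.** There is none for PPCs. The primary sample size does reproduce: with 76% and 38%, two-sided alpha 0.05 and 90% power, n = [1.96 × √(2 × 0.57 × 0.43) + 1.2816 × √(0.76 × 0.24 + 0.38 × 0.62)]² / 0.38² = (1.372 + 0.829)² / 0.1444 = 33.5, so 34 per group as tabulated. It does not bear on the PPC model.

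**How often a chance imbalance arises.** Let the number of patients with the comorbidity be an independent binomial(40, 0.30) count in each arm. Ten points is 4 patients and 15 points is 6. The exact probabilities, in either direction, are P(|difference| ≥ 4) = 0.39 and P(|difference| ≥ 6) = 0.18. At 20% prevalence the first is 0.33, and at 10% it is 0.19.

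**What a 10-point imbalance does.** Take an overall PPC rate of 20%, prevalence 30%, covariate odds ratio 3 and no drug effect.
- Risk without the comorbidity is 1/7 (odds 1/6) and with it 1/3 (odds 1/2). Check: 0.7/7 + 0.3/3 = 0.20.
- The arm with 25% affected has risk 0.75/7 + 0.25/3 = 0.1905, odds 0.2353.
- The arm with 35% affected has risk 0.65/7 + 0.35/3 = 0.2095, odds 0.2651.
- Apparent odds ratio: 0.2353/0.2651 = 0.89.

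At 20% prevalence, with PPC rates of 10-40% and covariate odds ratios of 2-5, the range is 0.81 to 0.93.

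**Power gain.** Simulated trials, 40 per arm, likelihood-ratio test for group, marginal rates held fixed, comparing no covariate with one baseline covariate. Morphine equivalents are in neither model.

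| Assumed PPC rates | Baseline covariate | Power without → with |
|---|---|---|
| 40% vs 20% | yes/no, 30% prevalence, OR 2 | 51% → 52% |
| 40% vs 20% | yes/no, 30% prevalence, OR 3 | 50% → 53% |
| 40% vs 20% | continuous, OR 1.5 per SD | 51% → 52% |
| 40% vs 20% | continuous, OR 2 per SD | 54% → 56% |
| 40% vs 20% | continuous, OR 3 per SD | 52% → 60% |
| 40% vs 20% | continuous, OR 4 per SD | 51% → 63% |
| 20% vs 10% | yes/no, 30% prevalence, OR 3 | 25% → 27% |
| 20% vs 10% | continuous, OR 3 per SD | 24% → 29% |
| 20% vs 10% | continuous, OR 4 per SD | 25% → 31% |

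Differences between rows in power without the covariate are simulation noise: with 3,000 trials the standard error is √(0.25/3000), about 0.9 points.

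**Standard error.** An expected-information calculation (control rate 20%, yes/no covariate at 20% prevalence with OR 3, conditional treatment OR 0.5) gives a standard error of the treatment log odds ratio of 0.636 without the covariate and 0.648 with it. The log odds ratio itself moves from -0.669 to -0.693, so power goes from 18.2% to 18.7%. Over control rates of 10-40% and covariate odds ratios of 2-5 the gain is 0.1 to 2.0 points. The variance of a standardised risk difference falls by 1% to 10%.

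**Room for covariates.** Rates of 20% vs 10% give 40 × 0.20 + 40 × 0.10 = 12 events, and 40% vs 20% give 24. That supports very few terms.

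**The case against.** The strongest reply is that little depends on this. The analysis is exploratory, the protocol admits that it is not sized for complications, and section III.B excludes patients whose disease severely limits respiratory function, which narrows the spread of any respiratory covariate. The larger power gains need a predictor with an odds ratio of 3 or 4 per SD. Between the 10th and 90th percentiles (2.563 SD) that is 3^2.563, about 17-fold, or 4^2.563, about 35-fold, in odds, and nothing in the documents supports such strength. With perhaps a dozen events, extra terms also carry a cost. All of this stands and sets the size of the point. It does not explain why respiratory comorbidity is used for length of stay and not for PPCs, and exchanging one covariate for another adds no parameter.

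A reader might also infer more than the documents support:
- That the plan loses precision. In logistic regression the standard error of the log odds ratio rises slightly with adjustment; the gain is in power and in a standardised risk difference.
- That leaving out baseline covariates biases the comparison. Randomisation keeps a comparison by group alone valid on average; imbalance matters for the one allocation that occurs.
- That an imbalance could match a drug effect. The assumed 40% vs 20% is an odds ratio of (0.20/0.80)/(0.40/0.60) = 0.375, far from 0.8-0.9.
- That the graft-outcome model shares the fault. Statistical Methods specifies no graft model, so there is no covariate list to criticise; that is a separate matter.

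**Conclusion.** The point holds as a minor one. The PPC model has no baseline covariate, its single adjuster is a post-randomisation quantity, and suitable baseline data are already collected and used elsewhere in the same plan. With 40 per arm, an imbalance of at least 10 points in a 30%-prevalence comorbidity is common (about 39% of trials), but its effect on the odds ratio is modest. The power to be gained is about 1 to 3 points for a yes/no comorbidity or a modest continuous predictor, and about 5 to 12 only for a very strong one. These sizes rest on assumed PPC rates, prevalence and predictor strength. The imbalance figure also assumes allocation not stratified on the covariate, which the documents do not describe either way. Whether treatment changes opioid use, and so whether the present adjustment distorts the PPC estimate, cannot be judged from the documents.

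**What to change.** Before unblinding, amend the PPC sentence in Statistical Methods so that any PPC is modelled on group and one named baseline covariate, either respiratory comorbidity (yes/no) or room-air SpO2, in place of total morphine equivalents. Use both only if the blinded, pooled event count permits, by a rule written in advance. Specify a penalised (Firth) fit with the same terms if events are few, and report a standardised risk difference with its confidence interval beside the odds ratio. Name the covariate in advance; do not extend to PPCs the primary model's clause on observed differences. If the sponsor prefers no baseline covariate, a sentence giving the reason would do. The cost is a few lines of SAP text: no new data, no added parameter and no change to trial conduct.

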Primary objective: To test the efficacy of NMBR with sugammadex, compared to neostigmine, to reduce inadequate NMBR and its related hypoventilation during the immediate postoperative period after kidney transplantation surgery, after adjusting for qTOF recovery and morphine equivalents received. We define hypoventilation as the incidence of ≥ 1 minute-long events of MV $<40\%$ of expMV. Minute ventilation will be measured continuously with a noninvasive respiratory volume monitor for the first 3h after the end of surgery or until meeting discharge criteria from the post-anesthesia care unit (PACU) (if sooner than 3h).

Secondary objective: To test the efficacy of NMBR with sugammadex, compared to neostigmine, to reduce inadequate NMBR and its related hypoventilation during the first 3 postoperative days in patients after kidney transplantation surgery, after adjusting for qTOF recovery and morphine equivalents received. We define hypoventilation as the incidence of ≥ 1 minute-long events of MV $<40\%$ of expMV. Minute ventilation will be measured continuously with a noninvasive respiratory volume monitor for up to 3d after surgery or until meeting end of monitoring criteria (if sooner than 3d)

Additional secondary objectives: To test if NMBR with sugammadex, compared to neostigmine, reduces patient's reported dyspnea scores (with the validated Patient-Reported Outcomes Measurement Information System, PROMIS®, assessment), decreases postoperative pulmonary complications (PPCs)

possibly related to inadequate NMBR after kidney transplantation surgery (i.e. respiratory insufficiency, gastric aspiration, pneumonia), improves kidney graft outcomes and reduces hospital resources utilization (i.e. hospital length of stay, ICU admission) and estimated healthcare costs.

II. Background and Significance/Preliminary Studies:

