- NMBR brief protocol: The sugammadex (intervention) or neostigmine (control) will be administered at the end of the surgery. The goal will be to administer the appropriate NMBR medication when ≥ 2 twitches are objectivized with the qTOF monitor. NMBR drugs and dosing for each group will follow standard of care FDA-approved doses, as follows: Sugammadex 2 mg/kg will be administered when spontaneous recovery has reached the reappearance of the second twitch in response to TOF stimulation.

	Sugammadex dosing (mg/kg)	Neostigmine dosing (mg/kg)
T4 recovered	2	0.03-0.05 (max 5 mg)
T2/T3 recovered	2	0.05-0.07 (max 5 mg)
T0/T4 with 1-2 post-tetanic twitches present or T1 recovered	4 or wait	Wait

Overdosing of neostigmine will be avoided to prevent neostigmine-induced muscle weakness. Neostigmine will be administered simultaneously with the appropriate glycopyrrolate dose (0.2 mg per 1.0 mg of neostigmine).

Extubation will be performed following the usual standard of care criteria of adequate level of consciousness, presence of airway protection reflexes and spontaneous ventilation parameters in addition to quantitative TOF $T4/T1 >0.9$. The following times (minutes) will be recorded: NMBR administration-to-T4/T1 >0.9 , NMBR administration-to-extubation, total operating room time.

Postoperative in-hospital phase

The blinded investigator will collect the following study-related information:

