- The blinded investigator will assess the presence of residual NMB with the quantitative TOF monitor by calculating the average of 3 measurements of qTOF $T4/T1$ (40mA or adequate to achieve TOF response while comfortable for the patient) within 15min of PACU arrival and hourly until up to 3h after the end of surgery or sooner if the patient meets PACU discharge criteria. We will record the initial PACU TOF and calculate the PACU average TOF. After transfer to the postoperative floor, the blinded investigator will assess residual or recurrent NMB with the qTOF monitor twice a day, with 3 repetitions each time, and each assessment separated by ≥ 6 h. This will be maintained for up to 3 days after the end of surgery or until end of monitoring criteria are met.
- The individual doses of administered opioids received by the patient during the study (PACU and daily for up to 3 postoperative days or until the end of monitoring criteria are met) will be recorded and converted to morphine equivalents[21] to statistically evaluate the effect of opioid administration on hypoventilation events.
- Nursingcharted episodes of respiratory depression during the PACU stay will also be recorded. Postoperative pulmonary complications (as defined elsewhere[13]) during PACU and up to 3 postoperative days will be collected.

Postoperative end of study follow-up

At postoperative day 14 ± 3 during the patient's visit to the transplant surgery clinic or via a phone call, the PROMIS® Dyspnea Functional Limitations Short Form questionnaire will be repeated

and normalized to the patient's baseline. Any postoperative pulmonary complications[13] and hospital resources utilization occurring from the hospital discharge until this end of study follow-up will be collected from the patient and the medical record, and the estimated costs based on average hospital daily stay depending on type of care unit or reported cost of complications calculated.

Any signs and symptoms of hypersensitivity (e.g. rash, anaphylaxis) detected during PACU and up to 3 postoperative days will be collected from the patient and patient's providers. The relationship of these signs and symptoms to sugammadex will be assessed by the patient's providers and also by the study safety officer. Their confirmatory diagnostic testing and management will be performed at the discretion of the patient's providers.

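### The planned pulmonary-complication, length-of-stay and cost models adjust for opioid dose given after the study drug, so they do not in general estimate the total drug effect that the objective asks for

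*Combined protocol and SAP*

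**What the plan says.** In III.F Statistical Methods, the PPC model is a logistic regression on any complication that "will include covariates for group and total morphine equivalents". The next sentence says "Hospital length of stay and costs will be compared between groups using a linear regression model"; its full specification is a "linear regression model including covariates for group, total morphine equivalents, presence of respiratory comorbidities and other clinical differences that may influence the outcome". No unadjusted or baseline-only analysis of these three outcomes is planned.

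The entry on morphine equivalents in III.F Variables/Time Points of Interest fixes the window: "This morphine equivalent dose will be calculated for the PACU period and daily for 3 first postoperative days", or until monitoring ends. III.C, Postoperative in-hospital phase, gives the source as "The individual doses of administered opioids received by the patient during the study" and limits it in brackets to the same period.

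On timing, III.C Preoperative phase states "Randomization will occur after patients consent for the study", and the reversal protocol under Intraoperative phase states "The sugammadex (intervention) or neostigmine (control) will be administered at the end of the surgery".

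The relevant objective, under Additional secondary objectives, begins "To test if NMBR with sugammadex, compared to neostigmine, reduces patient's reported dyspnea scores" and goes on to PPCs, graft outcomes, resource use and cost. It mentions no adjustment. The two hypoventilation objectives above it do specify adjustment for TOF recovery and opioids received.

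**The concern.** A covariate measured after the randomised treatment can carry part of that treatment's effect. It can also share unmeasured causes with the outcome, such as pain or a difficult operation. Conditioning on it removes whatever part of the drug effect runs through opioid dose. If the drug shifts the dose, conditioning also brings in an association through the shared causes, which randomisation had balanced. The group coefficient may then be too large or too small, or differ from zero when the drug does nothing to the outcome.

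At stake is what the trial will report on complications, stay and cost. A reader will take the group coefficient as the answer to the stated objective. Changing the primary model would not repair this, because these models are specified in separate sentences.

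**Working it through.** **1. The plan's own figures.** The documents give no figure for the PPC, stay or cost models. The only sample-size calculation concerns the primary outcome, and it reproduces with the pooled two-proportion formula (two-sided 0.05, 90% power, 76% vs 38%):

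n = [1.96·√(2·0.57·0.43) + 1.2816·√(0.76·0.24 + 0.38·0.62)]² / 0.38² = (1.372 + 0.829)² / 0.1444 = 33.5, so 34 per group.

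That is 40 less 6 dropouts. Nothing in it depends on opioid dose or on the models discussed here.

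**2. Order of events.** Consent, then randomisation, then surgery, then the reversal drug at the end of surgery, then PACU and floor opioids. Every dose in the covariate's stated window falls after the study drug.

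**3. Can the drug alter the covariate?** Variables/Time Points of Interest requires an average TOF ratio below 0.9 to be reported at once to the care team. Power/Sample Size works with 36% residual block after neostigmine (9 of 25 local patients) and 5% as the reduced rate. With 40 per arm that is 40 × 0.36 = 14.4 against 40 × 0.05 = 2 patients triggering a report. Section II notes that these patients are at increased risk of opioid-induced respiratory depression. An effect of the reports on opioid dosing is therefore plausible, though not documented.

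**4. Can the outcomes alter the covariate?** Opioid collection stops when monitoring stops. Under III.C that means discharge, or free ambulation without signs of respiratory complications, swallowing problems or weakness. Within the three days, a patient discharged early contributes fewer days of opioid, and one with a respiratory complication may contribute more. The total can thus depend on stay and on PPC status.

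**5. Size, no true drug effect (assumed inputs).** Let T be arm, U an unmeasured shared cause, M opioid dose and Y a continuous outcome such as stay, with within-arm SD 1:

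M = aT + rU + error; Y = rU + error.

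The adjusted coefficient of T is −a·r². Its standard error with 40 per arm is about √(2/40)·√(1 − r⁴)·√(1 + a²/4). Entries are absolute bias in SD and simulated type I error.

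| Shift a (SD) | r = 0.3 | r = 0.5 | r = 0.7 |
|---|---|---|---|
| 0 | 0; 5% | 0; 5% | 0; 5% |
| 0.1 | 0.009; 5% | 0.025; 5% | 0.049; 6% |
| 0.2 | 0.018; 5% | 0.050; 6% | 0.098; 8% |
| 0.3 | 0.027; 5% | 0.075; 6% | 0.147; 11% |
| 0.5 | 0.045; 5–6% | 0.125; 8% | 0.245; 22% |

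Hand check of the last cell: 0.5 × 0.49 = 0.245; SE = 0.2236 × 0.872 × 1.031 = 0.201; ratio 1.22; rejection about Φ(−1.96 + 1.22) = Φ(−0.74) = 23%, against 22% simulated. The unadjusted comparison stays at 5% throughout.

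**6. Direction, with a true effect (assumed inputs).** Take a direct drug effect of −0.5, an opioid effect of +0.5 per SD, and optionally a shared cause with r = 0.7.

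- Opioid shift −0.3 SD: total effect −0.5 + 0.5 × (−0.3) = −0.65. The adjusted coefficient is −0.50, or −0.5 + 0.3 × 0.49 = −0.35 with the shared cause.
- Opioid shift +0.3 SD: total effect −0.35. The adjusted coefficient is −0.50, or −0.65 with the shared cause.

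For PPC as a binary outcome, the same values on the log-odds scale with the shared cause give unadjusted versus adjusted odds ratios of 0.58 versus 0.71 at −0.3 SD, and 0.75 versus 0.54 at +0.3 SD. The error can go either way.

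**The case against.** The strongest reply is that the documents report no effect of the reversal drug on opioid dose. The trial is double-blind and the ventilation monitor is hidden from providers, which narrows the route from drug to dosing. If the dose does not shift, the linear models are unbiased and adjustment gains a little precision. This stands as a limit on the claim. A reader might infer that the models cannot estimate the drug effect at all; the documents do not support that. Nor do they secure the opposite, because low TOF ratios go to the care team.

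A reader might also take 22% as the expected type I error. It is the extreme corner of an assumed grid, and much of that grid sits at 5 to 6%.

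The analyses are labelled exploratory under Multiplicity, and the Clinical Hypotheses and III.E say that the trial is not sized for complications. That lowers the stakes. It does not make the coefficient answer the stated objective.

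Statistical Methods does not restate the window for total morphine equivalents, and the variable's definition mentions only the logistic regression. Still, PACU to day 3 is the only definition given. The confounder rationale in Statistical Methods concerns hypoventilation, so it does not justify the covariate here.

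**Conclusion.** The point holds in qualified form. By the plan's own definitions the opioid covariate is measured after the study drug, and it can depend on the drug and on the outcomes. The PPC, stay and cost models therefore do not in general estimate the total effect of sugammadex versus neostigmine. In the linear models the discrepancy vanishes if the drug leaves opioid dose unchanged; in the logistic model the odds ratio is then conditional on opioid dose. For a continuous outcome, the illustration gives a bias from zero to about 0.25 SD and a type I error from 5% to about 22%, depending on an assumed opioid shift and shared-cause correlation that the documents do not supply. It leaves out the dependence of opioid collection on discharge and recovery. The consequence is for interpretation of exploratory results. A reader should not infer any effect on the primary sample size.

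**What to change.** In Statistical Methods:

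- Remove total morphine equivalents from the main PPC, length-of-stay and cost models.
- Analyse PPC by group alone, or by group plus pre-specified baseline covariates. Respiratory comorbidity is at present named only for stay and cost, so it would have to be added if wanted for PPC.
- Analyse stay and cost by group plus baseline respiratory comorbidity, and limit the open-ended clause on other clinical differences to variables fixed before randomisation.
- Report opioid dose by arm as an outcome.
- Keep an opioid-adjusted model, if wanted, only as a labelled sensitivity analysis, stating its window and that collection can end at discharge or recovery.

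This changes analysis-plan wording only and needs no new data, patients or procedures. The price is some precision if opioid dose predicts the outcome and is unaffected by the drug. In the illustration with no shift, the standard error without adjustment is √(2/40) = 0.224 SD, against 0.217 with adjustment at r = 0.5 and about 0.195 at r = 0.7, so about 3% and 15% larger. Pre-specified baseline covariates may recover part of this.
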